5.17 Treatment of Anaphylaxis

Epinephrine is the treatment of choice for anaphylaxis. Aqueous epinephrine, 0.01 mg/kg (maximum dose, 1.5 mg) administered intramuscularly every 5 to 15 minutes as necessary, is the recommended dosage for controlling symptoms and maintaining blood pressure. The 5-minute interval between injections can be liberalized to permit more frequent injections if deemed necessary by the clinician. Epinephrine may be administered subcutaneously or intramuscularly. Intramuscular administration of injectable epinephrine in the anterior lateral thigh is preferred over subcutaneous injection.

Intravenous epinephrine is an option for patients with severe hypotension or cardiac arrest unresponsive to intramuscular doses of epinephrine and fluid resuscitation. Although there is no precisely established dosage or regimen for intravenous epinephrine in anaphylaxis, 5 to 10 mg intravenous bolus (0.2 mg/kg) doses for hypotension and 0.1 to 0.5 mg administered intravenously in the presence of cardiovascular collapse have been suggested. Other treatments should be combined with epinephrine such as: fluid resuscitation, recumbent posture, oxygen, inhaled adrenergic agents, vasopressors, H1 and H2 histamine receptor antagonists,

corticosteroids, and glucagon for individuals on β adrenergic blocking agents. (Sampson et al. 2006)

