3.7.2 SYN023

After thorough wound sanitation, injections of the entire calculated dose of SYN023 should be administered into and around all the bite wounds on Study Day 1. The dose of SYN023 should be calculated based on body weight: 0.3 mg/kg. For example, a 70 kg person has a calculated dose of 21 mg. The entire calculated dose should be given. Doses up to 3 mL may be given at a single injection site. Care must be taken NOT to administer a rabies vaccine near the Study Drug administration site.

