3.12.2 Pre-Study Drug and Post-Study Drug Monitoring of Subjects

Hypersensitivity reactions are a potential adverse effect both Study Drugs administered in this protocol. Allergic reactions to vaccination are also possible. Therefore, appropriate drugs and medical equipment to treat acute anaphylactic reactions must be immediately available and a medically qualified study team member trained to recognize and treat anaphylaxis must be present in the clinic during the entire Study Drug and vaccination procedure and post-vaccination monitoring period. Appropriate drugs include intravenous fluids, epinephrine, antihistamines, corticosteroids, inhaled oxygen and drugs required for the treatment of cardiac arrest such as antiarrhythmics and pressors. Appropriate equipment includes devices for blood pressure monitoring, oximetry, maintenance of airway and intratracheal intubation and, removal of secretions and cardiac defibrillation.

Subjects will have vital signs and oximetry taken prior to Study Drug administration. Before after and between each medicinal product administration vital signs and oximetry will be monitored every 30 minutes. At every clinical contact the subject will be asked how they are feeling and if they have noticed any new adverse symptoms or manifestations.

Subjects will remain in the clinic under close observation for at least 60 minutes after receiving rabies vaccination that is administered after Study Drug. Vital signs and oximetry will be repeated every 30 minutes during and at the end of the monitoring period before subjects leave the clinic.

Electrocardiograms are performed as a baseline to monitor subject safety (Table 3-1 and 3-2). Laboratory evaluations for subject safety are clinical chemistry evaluations, CBC, platelet counts and differential counts, PT (INR) and PTT and urinalyses. Please refer to Table 3-1 and 3-2 for a list of laboratory tests for monitoring of safety. Window intervals for specimen collection are also listed in Table 3-1 and 3-2.

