5.13 Adverse Event Treatment, Follow-up, and Outcome

Treatment of any adverse events will be determined by the investigator using his/her best medical judgment and according to current clinical practice guidelines. All applied measures as well as follow-up will be recorded in the appropriate CRF.

Adverse events will be considered resolved when the condition returns to normal or returns to the subject's baseline status as established on Study Day 1, or when the condition has stabilized with the expectation that it will remain chronic.

The investigator will continue follow-up on adverse events, including laboratory abnormalities and solicited adverse events, until the event has resolved, is otherwise satisfactorily explained, or the subject completes the study.

Follow-up for serious adverse events must continue until resolution and the outcome reported to the sponsor, even if this extends beyond the serious adverse event reporting period (i.e., after the final study visit). For analysis purposes, the outcome for serious adverse events will be determined on the final study visit.

Outcome of all adverse events will be classified as one of the following:

- Resolved
- Resolved with sequelae
- Ongoing
- Death

If at any time after completion of the serious adverse event reporting period (the final study visit) the investigator becomes aware of a serious adverse event that is suspected by the investigator to be related to the Study Drug, the event must be reported to the sponsor.

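### Section 5.17 prints the intravenous epinephrine bolus for hypotension at 20 to 50 times its own dose for cardiovascular collapse; the unit is very probably wrong

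*Protocol*

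**What the plan says.** Section 5.17 gives three epinephrine doses.

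- Intramuscular, first line: "Aqueous epinephrine, 0.01 mg/kg (maximum dose, 1.5 mg) administered intramuscularly every 5 to 15 minutes as necessary, is the recommended dosage".
- Intravenous, for hypotension and for collapse: "5 to 10 mg intravenous bolus (0.2 mg/kg) doses for hypotension and 0.1 to 0.5 mg administered intravenously in the presence of cardiovascular collapse".

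The intravenous route comes second: "Intravenous epinephrine is an option for patients with severe hypotension or cardiac arrest unresponsive to intramuscular doses of epinephrine and fluid resuscitation". The dosing sentence opens with a caveat, "Although there is no precisely established dosage or regimen for intravenous epinephrine in anaphylaxis", and presents the figures as suggestions. The section ends by citing the summary report of an anaphylaxis symposium. No other part of the protocol or SAP repeats or corrects the intravenous dose.

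Two other sections bear on how the text would be used. Section 5.13 says "Treatment of any adverse events will be determined by the investigator using his/her best medical judgment and according to current clinical practice guidelines". Section 3.12.2 requires that "a medically qualified study team member trained to recognize and treat anaphylaxis must be present in the clinic".

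**The concern.** The three doses treat one reaction in rising order of urgency, so they can be checked against each other. One would not expect the bolus for hypotension to exceed the dose for cardiovascular collapse given by the same route, nor to exceed the maximum for the slower intramuscular route. As printed it does both.

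The sentence is guidance to sites for an emergency that the protocol foresees: "Hypersensitivity reactions are a potential adverse effect both Study Drugs administered in this protocol". A wrong dose there matters more than a slip in background text, because it would be read when there is least time to question it.

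**Working it through.** **Inputs**

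- Intramuscular dose 0.01 mg/kg, maximum 1.5 mg (Section 5.17).
- Intravenous dose for hypotension 5 to 10 mg, also given as 0.2 mg/kg (Section 5.17).
- Intravenous dose for collapse 0.1 to 0.5 mg (Section 5.17).
- Example adult weight 70 kg (Section 3.7.2: "For example, a 70 kg person has a calculated dose of 21 mg").

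The plan derives none of these doses, so there is no calculation of its own to reproduce.

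**1. Hypotension bolus against the intramuscular dose**

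- Per kg: 0.2 / 0.01 = 20.
- Against the maximum: 5 / 1.5 = 3.3 and 10 / 1.5 = 6.7. The maximum applies only from 1.5 / 0.01 = 150 kg, so for most adults this understates the gap.
- At 70 kg the intramuscular dose is 0.01 × 70 = 0.7 mg. Then 5 / 0.7 = 7.1 and 10 / 0.7 = 14.3.

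**2. Hypotension bolus against the collapse dose**

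- Low end to low end: 5 / 0.1 = 50.
- High end to high end: 10 / 0.5 = 20.
- Opposite ends: 5 / 0.5 = 10 and 10 / 0.1 = 100.

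The like-for-like range is 20 to 50. The range of 10 to 100 pairs opposite ends and gives only the outer limits.

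**3. Which figure is out of place**

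At 70 kg the collapse dose is 0.1 / 0.7 = 0.14 to 0.5 / 0.7 = 0.71 of the intramuscular dose. The intravenous dose for the worst state is therefore below the intramuscular dose. The hypotension dose, by the same route for a lesser state, is above both. Its absolute and per-kg figures err in the same direction, which fits a wrong unit better than a mistyped digit.

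**4. A unit 1000-fold smaller (assumption)**

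The hypotension bolus becomes 0.005 to 0.010 mg.

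- Collapse over hypotension, like for like: 0.1 / 0.005 = 20 and 0.5 / 0.010 = 50. At the extremes it is 0.1 / 0.010 = 10 and 0.5 / 0.005 = 100.
- Intramuscular at 70 kg over hypotension: 0.7 / 0.010 = 70 and 0.7 / 0.005 = 140.

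The doses now rise from hypotension to collapse, and both intravenous doses lie below the intramuscular one. The numerical gaps do not close; the bolus now lies well below the other doses instead of above them. The smaller unit gains support from the order of the doses, not from closeness in size.

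**5. Absolute against per-kg figure (separate and minor)**

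5 / 0.2 = 25 kg and 10 / 0.2 = 50 kg, whereas 0.2 × 70 = 14. The two figures agree only at 25 to 50 kg. The mismatch is the same in any unit, so it says nothing about which unit is right.

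**6. How often the text might be used**

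Table 2.3-1 plans 5 + 30 + 184 = 219 HRIG recipients. At the protocol's 1 in 20,000 (Section 1.6), expected anaphylaxis cases are 219 / 20,000 = 0.011. If SYN023 had the same rate (assumption), all 448 subjects give 448 / 20,000 = 0.022. Vaccine reactions are left out. Cases that reach the intravenous step would be fewer.

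**The case against.** The strongest objection is that the point turns on one character before the g, printed twice in machine-read text, and a misread micro sign would not be an error in the plan. This cannot be excluded without the PDF, but it is unlikely. The micro sign is kept in the tissue-binding text of Section 1.3, and a Greek beta is read correctly in Section 5.17 itself. The plain u in the Appendix B units is weaker evidence, since that table comes from outside guidance and may have been typed that way.

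A second objection is that the right figure lies in a cited report that is not available here. That limits what can be proposed as a replacement. It does not remove the inversion, which is visible within the section.

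A third is that the text hedges, comes second-line, and sits under the investigator's judgment, current guidelines and the presence of trained staff. All of this stands, and it lowers the likelihood of harm. None of it corrects the figure: the safeguards work only if a clinician recognises the number as wrong and overrides it.

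A reader might infer that the protocol orders a dangerous dose for its subjects. It does not; it reports suggested doses for an optional step. A reader might also infer that the correct unit is the microgram. The documents do not say so; the smaller unit only restores the order of the doses.

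**Conclusion.** Wrong as written: very probably a unit error in site-facing safety guidance. The hypotension bolus is 20 times the intramuscular dose per kg, above the 1.5 mg intramuscular maximum, and 20 to 50 times the collapse dose like for like.

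The conclusion rests on two assumptions: that cardiovascular collapse is the more severe state, so its intravenous dose should not be the smaller, and that the text reproduces the issued protocol. It should not be taken as a finding that subjects are likely to be harmed. There is no effect on design, endpoints or analysis.

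**What to change.** First confirm that the issued protocol PDF prints mg in the hypotension part of the sentence. If it prints a smaller unit, no change is needed.

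If it prints mg, do one of the following:

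- correct both hypotension figures, absolute and per kg, to the cited consensus report; or
- delete the intravenous figures and refer to Section 5.13 and current anaphylaxis guidelines.

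Then notify sites. No replacement dose is proposed here, because the documents do not contain one. If the figures are kept, the mismatch between the range and the per-kg value can be checked against the same source.

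The cost is a check of one sentence and, if confirmed, a one-sentence correction and a short site notice.

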5.18 Recognition and Evaluation of Immune Complex Illness

Simultaneous presence of antibodies directed at circulating antigens may result in illness. Immune complex illness (ICI) results from the deposition of antibody-antigen complexes on the microvasculature with the resulting activation of complement and release of inflammatory mediators and tissue injury. These manifestations may result when anti-rabies antibodies such as those in RIG are administered in temporal proximity to rabies vaccine. They may also result when repetitive vaccination induces antibodies to the administered antigens. ICI manifests itself with inflammation and evidence of vascular injury. Syndromes of allergic vasculitis (leukocytoclastic vasculitis or Henoch-schonlein vasculitis in the case of IgA) and glomerular injury may be observed. Clinical manifestations of headache, anorexia and fever occur early followed by a petechial rash (palpable purpura) or larger purpura and cutaneous edema more frequent in the dependent regions of the body. Joint pain, rash and abdominal pain are common. The urinary findings may reflect an active glomerular process with hematuria, proteinuria and RBC casts. Acute glomerular histologic lesions of hypercellularity, necrosis, crescent formation and leukocyte infiltration are seen. Ultimately a reduction in renal function and elevated serum creatinine reflects this glomerular damage. ICI is treated by the cessation of antigen or antibody administration or the suppression of endogenously produced antigen. Prednisone has been used in the treatment of ICI (Salmon 2012).

6 PAUSING AND STOPPING RULES

These rules govern the pausing and stopping of Study Drug administration at any time during the study such as between doses (for multiple dose studies) for an individual, between individuals within a single dose group, and between dose groups.

6.1 DSMB Efficacy Pausing Rules

6.1.1 Confirmation of Initial LRG Pharmacodynamic activity

If the RVNA is found to be not adequate in the SYN023 initial LRG enrollment population then general LRG enrollment at that site will not be permitted by the DSMB until this has been resolved (Section 5.1.5.2).

6.1.2 Confirmation of Rabies in Trial Participants

Any laboratory confirmed or clinically suspected case of rabies occurs in the blinded trial the administration of Study Drug will be paused for DSMB confirmation of rabies diagnosis and review. The DSMB must confirm rabies in a case of the per protocol population before

unblinding of that case is considered. If a confirmed case of rabies occurs in the per-protocol unblinded SYN023 treated group the DSMB will issue a written communication permanently stopping enrollment and Study Drug administration. A rabies case will not be reported as an adverse event since it is an element of the primary objective.

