2.2.5 Advancement from LRG General Enrollment to the Normal Risk Group (NRG)

If Study Day 99 efficacy (RVNA) and safety LRG data from the initial and general enrollment have been judged to be adequate by the DSMB and there are no cases of rabies in SYN023 recipients by Study Day 183 then randomization into the NRG will be permitted (Section 5.1.5.3). It is presumed that a case of clinical rabies in the study population would become known to the DSMB promptly. Clinical rabies follow-up of the LRG will be made available to the DSMB through 6+ months on all patients for consideration of NRG commencement. The 12 months of LRG follow-up will not have ended when NRG enrollment starts.

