5.8 Assessing “Seriousness” and Serious Adverse Events

Seriousness refers to the outcome of an adverse event. Seriousness is determined by both the principal investigator and the local medical monitor. If either principal investigator or local medical monitor determines an event to be serious, it will be classified as such. If any of the following outcomes are present then the adverse event is serious:

- It results in **death** (i.e., the AE caused or led to the fatality). Serious does not describe an event which hypothetically might have caused death if it were more severe.
- It was immediately **life-threatening** (i.e., the AE placed the subject at immediate risk of dying. It does not refer to an event which hypothetically may have led to death if it were more severe).
- It required inpatient **hospitalization** or prolonged hospitalization beyond the expected length of stay. Hospitalizations for scheduled treatments and elective medical/surgical procedures related to a pre-existing condition that did not increase in severity or frequency following receipt of Study Drug, are **not** serious by this criterion. Hospitalization is defined as a hospital admission or an emergency room visit for a period greater than 24 hours.
- It resulted in a persistent or significant **disability/incapacity** (i.e., substantial reduction of the subject's ability to carry out activities of daily living).
- It resulted in a **congenital anomaly or birth defect** (i.e., an adverse finding in a child or fetus of a subject exposed to the Study Drug prior to conception or during pregnancy).
- Other **medically important conditions** that may not result in death, threaten life or require hospitalization (i.e., the AE does not meet any of the above serious criteria) may be considered a serious adverse event when, based on appropriate medical judgment, they may jeopardize the subject and require medical or surgical intervention to prevent one of the

serious outcomes listed in these criteria (e.g., allergic bronchospasm requiring intensive treatment in an emergency room or at home; blood dyscrasias or convulsions that do not result in hospitalization, or the development of drug dependency or drug abuse).

A **serious adverse event** is an adverse event meeting the outcome criteria for seriousness regardless of relationship to an administered medicinal product.

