5.11 Reporting of Serious Adverse Events

Serious adverse events, which include SUSARs, are reported to the sponsor and to the pharmacovigilance (PVG) for the entire study period (see protocol appendix A).

Pharmacovigilance (PVG), PPD Global Ltd.
24 Hour Safety [contact]
24 Hour Safety Hotline [contact]
[contact]

SUSARs are reported even after the trial is over, if the sponsor, local medical monitor or principal investigator becomes aware of them. The site will be provided with specific reporting procedures including the Adverse Event CRF and any supplemental reporting forms to be used. Serious adverse events will be reported on the Adverse Event CRF using a recognized medical term or diagnosis that accurately reflects the event.

Serious adverse events will be assessed by the investigator and the local medical monitor according to their roles (as described in Sections 5.1.1 and 5.1.3) for severity, causal relationship

to the Study Drug, and expectedness. The onset and resolution dates of the event and the action taken in response to the event will be documented. If the event has not resolved by the final study visit, it will be documented as “ongoing” on the CRF, however, follow-up of the SAE must continue until resolved. Information recorded on the CRF must be substantiated in the source documents.

The SAE Report form completed for that event must be faxed by the principal investigator or his/her designee, within 24 hours (one calendar day) of the clinical site becoming aware of the event, to the local medical monitor and to the Pharmacovigilance (PVG) at PPD (Appendix A). The AE CRF should be completed with all information known at the time; the Supplemental SAE Report (paper form) should be completed and both forms faxed (even if all information concerning the event is not yet known) within the first 24 hours of awareness of the event.

Fatal or life-threatening serious adverse events that the investigator suspects are related to the Study Drug should be telephoned to the local medical monitor immediately upon the investigator's awareness of the event. If the local medical monitor is required by the protocol or chooses to suspend enrollment s/he shall immediately create a written memorandum for record to the study file and telephonically notify the sponsor of this act.

Contact information for all safety personnel are contained in the Team Contact List which will be stored on site in the Site Regulatory Binder and maintained by the study sponsor.

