5.12 Immediately Reportable Events

These are events that might affect randomization or analysis. The investigator must report the following events by faxing the appropriate form to the local medical monitor within 24 hours of becoming aware of the event:

- Withdrawal of consent during the study (Immediately Reportable Event Form)
- Emergency unblinding (Immediately Reportable Event Form)
- Protocol violation affecting the safety of a subject or involving the vaccination process (Immediately Reportable Event Form)
- Adverse event thought to be an allergic reaction to the Study Drug (Immediately Reportable Event Form, unless event meets SAE criteria)
- Any event that, in the opinion of the investigator, precludes further administration of the Study Drug (Immediately Reportable Event Form, unless meets SAE criteria)
- Pregnancy (Immediately Reportable Event Form, and Pregnancy Notification Form)

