6.2 Safety Pausing Rules

The principal investigator and/or local medical monitor will pause administration of Study Drug in the trial if:

1. It is determined that a SUSAR occurred

OR

2. It is determined that a serious adverse event OR an adverse event pattern of grave concern occurred AND is judged to be POSSIBLY, PROBABLY or DEFINITELY related to Study Drug.

If the principal investigator and/or local medical monitor pauses administration of Study Drug in the study, he or she will record this in a memorandum to the study file and notify the sponsor who will then convene the DSMB. If additional clinical information becomes available during this pausing process that reduces the principal investigator's or local medical monitor's assessment of causality, severity or toxicity grade such that study pausing is no longer required by pausing rules, in other word if the PI or medical monitor recognizes their pausing of the study was in error, then the principal investigator, with the agreement of the medical monitor, and DSMB chairman/chairwoman may resume Study Drug administration, record this in a memorandum to the study file, and notify the sponsor.

Since the global medical monitor is unblinded and reviews data from all the sponsor's trials, he or she may become aware of an adverse event pattern of concern not appreciated by the principal investigator or local medical monitor. If the global medical monitor independently determines that an adverse event pattern of grave concern that is judged to be POSSIBLY, PROBABLY or DEFINITELY related to Study Drug has occurred, the global medical monitor will pause administration of Study Drug in the trial, record the study pause in a memorandum to the study file, and notify the local medical monitor, principal investigator and sponsor who will convene the DSMB.

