9.1.5. Death

All subjects who have an AE with an outcome of death will be presented in a listing.

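### Rabies cases are barred from adverse event reporting with no replacement route written, so the rabies pause has no reporting deadline and a rabies death would be missing from the SAE and death outputs

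*Protocol*

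**What the plan says.** On a rabies case, Protocol 6.1.2 says that "the administration of Study Drug will be paused for DSMB confirmation of rabies diagnosis and review". The same paragraph ends: "A rabies case will not be reported as an adverse event since it is an element of the primary objective".

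The general safety rules point the other way. Section 5.3 treats any unfavourable disease arising after treatment as an adverse event, and 5.8 makes such an event serious, if its outcome qualifies, "regardless of relationship to an administered medicinal product". Section 5.11 requires the SAE form to be sent "within 24 hours (one calendar day) of the clinical site becoming aware of the event", and has the sponsor notify the DSMB of SUSARs within 3 working days. Section 5.12 opens its separate 24-hour list with "These are events that might affect randomization or analysis".

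On how the DSMB would learn of a case, 2.2.5 says: "It is presumed that a case of clinical rabies in the study population would become known to the DSMB promptly".

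In the SAP, 9.1.5 reads: "All subjects who have an AE with an outcome of death will be presented in a listing". SAE listings and summaries (9.1, 9.1.2) are likewise drawn from adverse events. Rabies cases go to a table of counts in 8.1.1.4, prepared after DSMB confirmation.

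**The concern.** The rabies pause is the most consequential one in the trial. By 5.1.5.1, a case in the SYN023 per-protocol group fails the primary objective and ends dosing. A pause can start only when someone reports the event, and the sentence quoted from 6.1.2 closes the ordinary reporting channel without opening another.

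Timing adds to this. The protocol's rationale puts most incubation periods at 46 to 189 days. Unsolicited AE collection ends at Study Day 43 (3.12.1). When most cases would appear, SAE reporting is the only safety channel still open, and it is the one that 6.1.2 closes.

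The second stake is the safety report. A reader expects a death listing to contain every death. Under the rules as written, a death from the disease that the product is meant to prevent would not be in it.

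**Working it through.** There is no planned figure to reproduce. The check is to follow a rabies case through each reporting route and each output.

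**Reporting routes**

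- *SAE report, 5.11 (24 hours).* This covers serious adverse events. Section 5.8 defines an SAE as a kind of adverse event, so an event that may not be reported as an AE does not enter this route.
- *DSMB notice, 5.11 (3 working days).* This covers SUSARs only, which are a subset of SAEs. It is closed for the same reason.
- *Immediately reportable events, 5.12 (24 hours).* There are six items: consent withdrawal, emergency unblinding, certain protocol violations, suspected allergic reaction, an event that rules out more Study Drug, and pregnancy. Rabies is not listed, although a case plainly fits the list's stated purpose. The fifth item is left to the investigator's opinion and fits poorly, because Study Drug is given on Study Day 1 only.
- *Section 2.2.5.* This presumes prompt knowledge and sets no procedure.

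**Who imposes the pause**

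- 6.1.2 is in the passive voice and names nobody.
- 6.2 does name people: "The principal investigator and/or local medical monitor will pause administration of Study Drug in the trial if". Its triggers are a SUSAR, or a related SAE or AE pattern of grave concern.
- 5.1.1 gives the principal investigator authority to pause on suspicion of significant risk. That is a power, not a duty tied to rabies.
- 5.1.5.1 has the DSMB confirm the diagnosis and decide whether to stop.
- 5.1.5.5 convenes the DSMB after a pause by the investigator or either medical monitor. It cites 6.1 for the safety pausing rules, which are in 6.2.
- 5.11 says what the local medical monitor must record and telephone if the protocol requires enrolment to be suspended. It does not say that rabies is such a case.

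Several roles can pause or stop. No section assigns the 6.1.2 pause to one of them or sets a time for it.

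**SAP outputs for one fatal rabies case**

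- 8.1.1.4, table of rabies counts: present, after DSMB confirmation.
- 9.1 and 9.1.2, SAE listing and summaries: absent, because there is no AE record.
- 9.1.5, death listing: absent, because it requires an AE with a fatal outcome.
- 5.1, disposition: possibly present as a reason for discontinuation.

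**How likely a case is.** Protocol 7.8.5 puts the failure rate at p = 0.01% to 0.1%. The chance of at least one case in n subjects is 1 − (1 − p)^n.

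- n = 184 (NRG SYN023): 1 − 0.9999^184 = 1.8%; 1 − 0.999^184 = 16.8%.
- n = 229 (45 LRG + 184 NRG on SYN023): 2.3% to 20.5%.
- n = 448 (all subjects, assuming the same rate in both arms and both risk groups): 4.4% to 36.1%.

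**The case against.** Keeping an efficacy endpoint out of the AE tables can be legitimate. Section 6.1.2 gives its reason openly, and a specific exception may override a general definition. The case does not vanish: SAP 8.1.1.4 counts it, 8.2 refers to it again, and disposition may show it. Section 3.9.1 presumes that anyone alive and out of hospital does not have rabies. A live suspected case is therefore a hospitalised encephalitis, which a site might well file as an SAE before rabies is recognised. The stopping rule in 6.3 covers death in any subject without requiring an AE record. Section 2.2.5 also promises the DSMB rabies follow-up on the LRG. The DSMB charter and the site reporting procedures, which are not in these documents, may fill the gap.

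Much of this stands as qualification. None of it supplies the missing route. An SAE filed for undiagnosed encephalitis would be incidental, and because every subject has an exposure, a clinically compatible illness is already a probable rabies case under the protocol's own definition. The follow-up in 2.2.5 serves the decision to open the NRG and is not notice of individual cases in the NRG. Section 6.3 tells the DSMB what to do about a death but not how it learns of one. An endpoint exception needs its own reporting path, and the protocol should point to it if it lies elsewhere.

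Three stronger readings go too far:

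- *Late notice would lose the diagnosis.* Section 3.9.1 accepts post-mortem specimens, testing is local and starts when signs appear, and probable cases count without laboratory proof.
- *A definite number of extra subjects would be dosed before the pause.* The documents give neither an accrual rate nor a notification delay, so no count can be supported.
- *Nobody has power to pause.* Sections 5.1.1, 5.1.5.1, 5.1.5.5 and 5.11 give the investigator, the monitors and the DSMB some role. The fault is unclear assignment.

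**Conclusion.** The point holds as a gap in reporting and an internal conflict. As written, 6.1.2 contradicts 5.3 and 5.8 and removes rabies from the 24-hour SAE report. Sections 5.12 and 2.2.5 and the SUSAR clock do not replace that report. The pause has no reporting deadline, and its owner is unclear.

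On outputs, each fatal rabies case would leave the death listing and the SAE outputs one short while still being counted in SAP 8.1.1.4. This assumes that sites apply 6.1.2 literally and that no document outside the protocol and SAP sets another rule. The event is uncommon but not remote: 1.8% to 16.8% for at least one case among 184 NRG SYN023 recipients, if the sponsor's own failure rate is right. Sample size, alpha and the primary analysis are unaffected.

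**What to change.** 1. Add any clinically suspected, probable or confirmed rabies case to the 5.12 list, using its existing form and 24-hour route, with onward notice to the DSMB.
2. Change SAP 9.1.5 to list all deaths from any cause, whether or not an AE record exists.
3. Show rabies cases in the SAE listing, flagged as endpoint events.
4. Reconcile Protocol 5.3, 5.8, 5.11, 5.12, 6.1.2, 6.2 and 6.3, and the pausing roles in 5.1.1, 5.1.5.1 and 5.1.5.5, so that they agree on reporting and on who is responsible for the pause. Who that should be is for the sponsor to settle; this review proposes no one. Correct the cross-reference in 5.1.5.5 at the same time.

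The cost is a few lines in each document. The one small drawback is that a rabies case appears both in the efficacy table and in the SAE listing, which the flag explains.
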